### Treatment Regimen

Patients randomized into the treatment (antibiotic) arm of the study will be treated with a seven-day course of oral azithromycin and amoxicillin. Azithromycin will be dosed as single 500 mg dose immediately following randomization, yet prior to discharge to home, followed with 250mg each day for 4 more days. Amoxicillin will be dosed as 500mg orally three times daily for 7 days with its first dose also being given prior to discharge home.

Due to delayed result reporting for chlamydia, gonorrhea and trichomonas within the Woman's Hospital Laboratory, results of such testing will not be available at the time of randomization. Those pa-

tients testing positive for any of the aforementioned genitourinary infections will be treated according to standard guidelines.

Inclusion Criteria:

1. Singleton gestation
2. Gestational age of greater than 18 0/7 but less than or equal to 22 6/7
3. Diagnosis of prelabor premature rupture of membranes as determined by clinical examination noting either/or 1) visualization of amniotic fluid passing from the cervical canal and pooling in the vagina via sterile speculum examination, 2) a basic pH (i.e., positive nitrazine) test of vaginal fluid, 3) arborization (ferning) of dried vaginal fluid identified via microscopic examination, or 4) an amniotic fluid index (AFI) of less than 4cm.
4. Greater than or equal to 18 years of age
5. Those with no known drug allergies or significant adverse reactions to azithromycin or amoxicillin
6. Afebrile at the time of presentation and throughout 24-hour observation period
7. Patient must be able to provide informed consent

Exclusion Criteria:

1. Fetal anomalies
2. Diabetes mellitus, including both pre-gestational and gestational
3. Abnormal placentation
4. Poor dating with dating ultrasound performed later than or equal to 20 0/7 weeks
5. Current subchorionic hemorrhage or current vaginal bleeding on presentation
6. Hypertensive disease, including pre-gestational chronic hypertension, gestational hypertension and pre-eclampsia/eclampsia
7. History of amniocentesis during this pregnancy
8. History of cervical incompetence, history of cerclage in previous pregnancy or current cerclage in place
9. Current documented urinary tract infection or bacteriuria
10. Current documented genital tract infection (Chlamydia, gonorrhea, or trichomonas)

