
If, during the 24-hour observation period, the subject is without signs of chorioamnionitis††, pre-term labor‡, or placental abruption with vaginal bleeding as determined by the MFM staff, and if patient continues to meet both inclusion and exclusion criteria, subject will then be offered enrollment in the study. The consenting process will be performed by the MFM staff physicians or by [name], the co-investigator. The consenting process will be performed within the patient's private hospital room (designated at the time of admission). Once the subject has agreed to voluntary participation and informed consent has been signed, the subject will then be assigned an individual study identifier that includes the study acronym OAPPPROM patient initials, and unique number (randomly generated using the sample () function in R statistical software). All blood samples and specimens collected prior to admission, at admission and future blood samples and specimens will be available to the treating physician and reported within the patient's chart as is current standard practice. They will also be referenced using the patient's unique identifier for the sake of research data collection. The enrolled subjects will then be randomized using a computer-generated sample without replacement from the patient ID numbers into either the control (no antibiotics) or treatment (antibiotics) arm. Details for admission and inpatient management are outlined in Flowsheet 1 (see Appendix I).

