Following the 24-hour observation period and randomization, those subjects enrolled into the treatment (antibiotics) arm of the study will be thoroughly counseled on the risks and adverse side effects associated with the use of azithromycin and amoxicillin and which of those side effects should prompt emergency evaluation at Woman's Hospital Assessment Center or the nearest emergency department with obstetrical care. The subject will be counseled on the proper dosing: azithromycin (500mg day one followed by 250mg per day for 4 more days) and amoxicillin (500mg orally three times daily for 7 days) for a total course of seven days of antibiotic therapy. The first dose of both antibiotics will be given prior to discharge to home. Woman's Hospital's Retail Pharmacy will be contacted by the subject's nurse the morning of discharge (as indicated by MFM doctor on-call) to arrange for subject's enrollment in the "Meds to Beds" program. Involvement in this program will allow for the patient to have her medications and a thermometer delivered to her bedside prior to discharge, intending to foster increased compliance rates as it eliminates the need for pharmacy visits. The cost of the antibiotics will be covered by donations from the Maternal-Fetal Medicine department.

Subjects in both the treatment (antibiotics) and control (no antibiotics) arm of the study will be thoroughly counseled on symptoms or findings which should prompt immediately follow-up at Woman's Hospital or the nearest emergency department with obstetrical care. Such symptoms include, but are not limited to, vaginal bleeding, fevers, chills, purulent vaginal discharge, contractions, pelvic pain or cramping, abdominal pain or cramping, or any other concerns. Subjects will be required to have a thermometer available to them either at home or work in order to allow for daily temperature documentation. Thermometer will be provided by the Woman's Hospital Retail Pharmacy with the antibiotic prescriptions. The cost of the thermometer will be covered by donations from the Maternal-Fetal Medicine Department. Counseling on proper techniques for taking axillary/ oral temperatures will be provided by the consenting provider at the time of enrollment. Subjects will be counseled on avoidance of sexual intercourse and avoidance of overt exertion, yet, strict bed rest will not be advised. All subjects will receive a "Patient Information Pamphlet" (see Appendix III). Subjects will be instructed to keep this pam-

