All of the data collection sheets will be stored within a secure research binder. This binder will be kept secure in a locked desk drawer, within a locked office (MFM office located at [name]), when not in use. Access to study data will only be granted to [name] [name] and [name] during the study period. Following completion of the study, a final Excel spreadsheet will be created which will include all data previously collected, including the patient's unique identifier but excluding the patient's medical record number (de-identified). The final, compiled spreadsheet with de-identified data will be made available to [name] for final data analysis. Upon completion of finalized data spreadsheet, the hard copies contained within the designated research binder will be disposed of in a secured, locked shred bin on Woman's Hospital campus. The spreadsheet will be encrypted and stored on a password-protected and encrypted laptop, property of the investigator [name]. The spreadsheet will not be stored or saved onto any of the various, available internet storage services (i.e., DropBox, Google Drive, etc.)

If at any point during the study, subjects of either arm show signs of infection (fever, rigors, chills, pain), labor, abruption (vaginal bleeding), or fetal distress, subjects will be admitted to Woman's Hospital for induction of labor/delivery as recommended per established standards of care. Delivering physician will be either the patient's primary obstetrician or MFM specialist if subject received prenatal care at facility outside of Woman's Hospital.

If subject and her fetus show signs of continued stability with no adverse events/side effects, signs of chorioamnionitis, infection, labor, or placental abruption, from the time of rupture until 23 0/7 weeks gestation, the subject will be readmitted to Woman's Hospital's Labor and Delivery Unit at 23 0/7 for continued inpatient management until delivery. At the time of readmission, both treatment and con-

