trial arms will receive fetal neuroprotective magnesium sulfate (6 gram loading dose, 6g in 100mL infused over 15- 20 minutes, followed by maintenance dose of 2g/hour at rate of 50mls/hr of 20g/500mL for a minimum of 12 hours), betamethasone course for fetal lung maturity (12mg intramuscular administered every 24 hours for total of two doses), and latency antibiotics (erythromycin 500mg orally every 8 hours for seven days with 48-hour course of ampicillin 2g intravenously every 6 hours followed by amoxicillin 500mg orally every 9 hours for 5 days) as guided by current standard of care practices. Duration of treatment with magnesium sulfate will be standardized to a total of 12 hours on readmission and a plan for restart of medication if delivery is felt to be imminent and at a gestational age of less than 34 weeks. While subjects are receiving magnesium sulfate, routine evaluations to assess for signs of magnesium toxicity will be performed as is outlined in the hospital policy regarding magnesium administration in pregnancy. Briefly this includes monitoring for signs and symptoms of magnesium overdose and therapy with calcium gluconate as need for magnesium toxicity.

Other orders to be instituted at the time of readmission include a repeat culture of urine, complete blood cell count, Maternal Fetal Medicine consultation, fetal ultrasound, regular diet, IV with saline lock, bed rest with bathroom privileges and fetal non-stress testing twice per day. Obstetric ultrasounds will be repeated by the Maternal-Fetal medicine specialists within 24 hours of readmission and at least once every 7 days till delivery is indicated.

A rescue course of betamethasone (single dose of 12mg intramuscularly) will be administered if the subject does not deliver within 14 days of completion of the initial 2-dose course of betamethasone and if delivery is suspected within the next seven days.

Delivery following readmission will be at the discretion of the attending obstetrician in regards to evidence of maternal or fetal infection, labor, non-reassuring fetal assessment or placental abruption in addition to any other standard indication for delivery (ie., pre-eclampsia) or if patient reaches 34 0/7 weeks gestational age. Route of delivery will be determined by routine obstetrical indications.

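### Dosing rules overlap at 23 0/7: treated women randomised late in week 22 and still stable would take two macrolides for 1–4 days, and redundant beta-lactams for 1–6 days

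*Protocol*

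**What the plan says.** **Outpatient course.** Under Treatment Regimen, azithromycin starts with 500 mg directly after randomisation, "followed with 250mg each day for 4 more days". The companion drug is set out as "Amoxicillin will be dosed as 500mg orally three times daily for 7 days with its first dose also being given prior to discharge home". Methods repeats both schedules in the counselling text, "for a total course of seven days of antibiotic therapy".

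**Entry window.** Inclusion criterion 2 is "Gestational age of greater than 18 0/7 but less than or equal to 22 6/7". Randomisation follows a 24-hour observation period, and eligibility is checked again then: "if patient continues to meet both inclusion and exclusion criteria, subject will then be offered enrollment in the study".

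**Readmission.** Under Methods, a woman who has stayed stable is readmitted to the "Labor and Delivery Unit at 23 0/7 for continued inpatient management until delivery". Both arms then receive "latency antibiotics (erythromycin 500mg orally every 8 hours for seven days with 48-hour course of ampicillin 2g intravenously every 6 hours". The oral step that comes after the ampicillin is given as "followed by amoxicillin 500mg orally every 9 hours for 5 days". No exception is made for a woman whose study course is unfinished.

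**Stopping.** The Discontinuations section lists when study drug must stop: withdrawn consent; an adverse event, laboratory abnormality or illness that the investigator judges incompatible with continuing; or loss of the ability to consent freely. Readmission at 23 0/7 is not listed.

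**Intent.** The primary and secondary objectives and both endpoints describe the intervention as oral outpatient antibiotics given before 23 0/7.

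**The concern.** The outpatient course has a fixed length counted from randomisation. The inpatient course has a fixed start counted from gestational age. When randomisation falls less than a week before 23 0/7, the two run together, and the dosing text does not say which one gives way.

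What is at stake is a small matter of patient safety. A few treated women would receive two macrolides at once. Benefit/Risk and Ethical Assessment lists QTc prolongation, arrhythmia and torsade de pointes among macrolide effects, and Ethical and Regulatory Requirements repeats them for azithromycin. No exclusion criterion concerns cardiac rhythm. The same women would also have amoxicillin from two supplies, which serves no stated purpose.

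Routine follow-up may not catch this. Pills are counted at weekly clinic visits, and for a woman randomised at 22 1/7 or later a visit one week on falls after 23 0/7. The readmission orders listed under Methods include neither a pill count nor collection of leftover study drug.

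**Working it through.** The Protocol gives no figure of its own on this point, so the check is a calendar count.

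**Inputs (Protocol, Treatment Regimen and Methods).** Randomisation is day 1. Azithromycin covers days 1–5 (1 + 4) and outpatient amoxicillin days 1–7. From 23 0/7, erythromycin runs for 7 days, ampicillin for the first 2 days, and inpatient amoxicillin for the next 5.

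**Days left at 23 0/7.** A woman randomised at 22 k/7 reaches 23 0/7 on her day 8 − k. The days remaining, counting 23 0/7 itself, are:

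- amoxicillin: 7 − (8 − k) + 1 = k
- azithromycin: 5 − (8 − k) + 1 = k − 2, or 0 if that is negative

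| Randomised at | Azithromycin with erythromycin (days) | Outpatient amoxicillin with ampicillin (days) | Outpatient with inpatient amoxicillin (days) | Total beta-lactam overlap (days) |
|---|---|---|---|---|
| 22 0/7 | 0 | 0 | 0 | 0 |
| 22 1/7 | 0 | 1 | 0 | 1 |
| 22 2/7 | 0 | 2 | 0 | 2 |
| 22 3/7 | 1 | 2 | 1 | 3 |
| 22 4/7 | 2 | 2 | 2 | 4 |
| 22 5/7 | 3 | 2 | 3 | 5 |
| 22 6/7 | 4 | 2 | 4 | 6 |

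If the first amoxicillin day is only partial and the 21 doses spill into an eighth calendar day, beta-lactam overlap starts at 22 0/7 and lasts 1–7 days. The macrolide column does not change.

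**Daily amoxicillin while both supplies run.** 3 × 500 = 1,500 mg outpatient, plus 500 × 24/9 = 1,333 mg inpatient with the 9-hour interval as written, gives 2,833 mg, or about 2.8 g.

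**How many women.** Entry strictly after 18 0/7 plus 24 hours of observation gives randomisation days 18 2/7 to 22 6/7, which is 33 days (34 if 18 0/7 itself is admitted). The Protocol does not give the distribution of entry; uniform entry is an assumption. With 17 treated women, all stable and undelivered at 23 0/7:

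- two macrolides (4 entry days): 17 × 4/33 = 2.1 expected (2.0 with 34 days)
- beta-lactam overlap (6 entry days): 17 × 6/33 = 3.1 expected (3.0 with 34 days)

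These are means. Under the same binomial model, more than 2 women have two macrolides with probability 0.34, and more than 3 have beta-lactam overlap with probability 0.37.

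Not everyone will still be pregnant and stable. Let s be the share who are, taken as 25–100% (assumption). The chance that at least one treated woman is affected is 1 − (1 − s × days/33)^17:

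| s | Expected, two macrolides | Expected, beta-lactams | P(at least one), two macrolides | P(at least one), beta-lactams |
|---|---|---|---|---|
| 25% | 0.5 | 0.8 | 41% | 55% |
| 100% | 2.1 | 3.1 | 89% | 97% |

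**The case against.** The strongest reply is that the Protocol already confines the intervention to outpatients before 23 0/7. Both objectives and both endpoints say so, and a woman readmitted at 23 0/7 is outside that definition. Overlap then needs ward staff to order both regimens, or an inpatient to keep taking her home pills. A Maternal-Fetal Medicine consultation is ordered at readmission, and the latency regimen is tied to standard care. The readmission pathway is also limited to women without side effects. Finally, the patient pamphlet (Appendix III) was not in the text available for review and might say what to do with leftover pills.

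Much of this stands. The intent is evident, and staff may well stop the home drugs unprompted. It does not close the gap, because wording in an objective or endpoint is not a dosing instruction, and the dosing text gives the woman a full seven-day course. Methods describes the pamphlet as holding logs, visit findings and contact details, and mentions no stopping instruction.

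A reader might also draw stronger conclusions that the document does not support:

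- *That the sections contradict each other.* They do not. Each dosing rule is clear by itself; what is missing is the rule for where they meet.
- *That 2 and 3 of 17 are upper limits.* They are expected values and can be exceeded by chance.
- *That doubling the beta-lactam is harmful.* The Protocol itself gives ampicillin at 8 g a day (4 × 2 g), so 1.5 g of amoxicillin adds about 19% (1.5/8) on those days, and nothing in it marks 2.8 g of amoxicillin a day as excessive.
- *That a woman presenting at 22 6/7 would start both regimens together.* After 24 hours she is at 23 0/7 and no longer meets inclusion criterion 2, which Methods requires her still to meet.

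**Conclusion.** The point holds as a minor one. Followed exactly, the dosing rules give azithromycin with erythromycin for 1–4 days to treated women randomised at 22 3/7–22 6/7. They give 1–6 days of redundant beta-lactam to those randomised at 22 1/7–22 6/7. Both apply only to women stable and undelivered at 23 0/7.

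The day counts follow from the Protocol alone. The numbers of women rest on two assumptions without a source in it: uniform entry and the share still pregnant and stable.

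The safety argument rests on the two macrolides only. The Protocol lists rhythm effects for the class but does not discuss combined use, so the added risk cannot be quantified. The beta-lactam overlap is redundant dosing with no harm shown. This is a cheap improvement at the lowest severity. Dosing belongs in the protocol, so the gap is not one to leave to a statistical analysis plan.

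**What to change.** Add one sentence in three places (Treatment Regimen, the counselling paragraph in Methods, and the readmission paragraph in Methods): *Any remaining outpatient azithromycin and amoxicillin are stopped when the inpatient latency regimen starts at 23 0/7.* If the patient pamphlet does not already say so, repeat it there.

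The cost is a short amendment, approved by both review boards as the Protocol requires for any revision. Sample size, endpoints, visits and analysis do not change.

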## **Study Endpoints and Assessments**

### **Primary Endpoint**

The primary efficacy endpoint is the difference in the latency period, defined as the number of days from the date of rupture of membranes to the date of delivery, between those receiving oral, outpatient antibiotic therapy prior to 23 0/7 weeks gestational age and those receiving no antibiotic therapy.

### **Secondary Endpoint**

The secondary efficacy endpoint is whether the subject reached viability (23 0/7 weeks gestational age) prior to delivery. Comparisons will be made in the difference in the number of patients reaching viability in the control arm (no oral, outpatient antibiotic therapy prior to 23 0/7 weeks gestational age) and the number of patients reaching viability in the treatment arm (oral, outpatient antibiotic therapy prior to 23 0/7 weeks gestational age).

## **Biological Sampling Procedures**

### **Laboratory Measures**

Initial specimen collections to be used as baseline determinants for enrollment eligibility include a catheterized urinalysis with or without reflex urine culture, an endocervical swab for gonorrhea, chlamydia, and trichomonal testing, wet prep (i.e., vaginitis panel), and complete blood cell count. Nitrazine testing, as well as arborization (ferning) analysis, will be used for diagnosis of PPROM.

A nitrazine test involves placement of vaginal fluid, that which is suspected to be amniotic fluid, onto a Nitrazine test strip (pH test strip). Blue coloration of the test strip after sampling indicates an alkaline pH in the range of 7.0 to 7.3 versus the normally acidic vaginal fluid (pH of 3.8-4.2). Results of nitrazine testing can be affected by multiple factors including, but not limited to, blood, seminal fluid, soap resulting in false positive results.

Arborization, or ferning, involves collecting fluid from the posterior fornix of the vagina using a cotton swab and placing onto a glass slide for further microscopic examination. Care should be taken to perform the collection without the use of lubricant jelly. The specimen should be allowed at least 10 minutes to dry before microscopic evaluation performed. A delicate ferning pattern on the glass slide indicates a positive test result. False-positives can be obtained if care not taken during evaluation; well-estrogenized cervical mucus or a fingerprint can lead to false positive results.

Urine sampling for urinalysis will be provided by a catheter sample collected by a trained nursing assistant or registered nurse. Sterile practices will be implemented during the sampling procedure. The collected urine sample will be immediately sent to the laboratory for further analysis with efforts to minimize the time to analysis in order to prevent falsely elevated bacterial counts (due to propensity for bacteria to continue to proliferate in warm medium). Findings of greater than 5 white blood cells, positive leukocyte esterase, bacteria present or positive nitrites would prompt further evaluation with reflex urine culture. Positive culture would be determined by greater than 100,000 colony-forming units (CFU) in an asymptomatic patient and greater than 100 CFU in symptomatic patients.

Endocervical sampling for gonorrhea, chlamydia, and trichomonas testing is to be performed by physician performing the initial evaluation at the time of suspected pre-viable PPRM. The Gen-Probe Aptima, or other alternative method or collection device as determined by the lab is the collection container, will be used for endocervical gonorrhea, Chlamydia, and trichomonas testing. Steps for collection include removal of excess mucus surrounding the cervical os, insertion of the specimen collection swab into the endocervical canal (no more than 0.5 centimeter into the canal), gentle rotation of the swab clockwise for 10-30 seconds, then placement of the swab into the transport tube (avoiding contact with vaginal walls at the time of swab removal). Sample can be stored at room temperature until the time of analysis. Nucleic acid amplification tests are then performed to determine the presence of gonorrhea, Chlamydia and trichomonal organisms.

The Wet Prep is also to be collected by the initial, evaluating physician at the time of PPRM diagnosis and analyzed by the Woman's Hospital lab. A cotton swab is used for vaginal collection. The specimen is then directly inoculated into the culture media. Microscopic evaluation of the specimen is then performed to determine the presence of clue cells indicative of bacterial vaginosis, yeast, and *Trichomonas*. Specimens can be received in the laboratory up to 48 hours after collection. Specimens must be incubated at 37 degrees Celsius if held for longer than 48 hours.

Complete blood count is collected via peripheral vein blood draw. A minimum of 0.5 milliliters of blood is to be collected into a lavender-top (EDTA) collection tube. After collection obtained, tube is to be inverted 8-10 times. Specimen is to be maintained at room temperature. Results are obtained using automated cell counter with mixed technologies.

At the time of re-admission at 23 0/7 weeks, group B strep DNA testing will be performed to determine need for future intrapartum prophylaxis if viability reached. Collection is performed using a cotton swab that is placed into the vaginal introitus then carried down toward the anus with insertion of the swab through the anal sphincter. A speculum should not be used for collection. The initial provider will perform the collection at the time of admission. Once collected, the specimen is stable for 24 hours at room temperature. Amies agar gel transport, a selective, enriched culture medium, is inoculated with specimen. If colony growth obtained, real-time PCR will be performed for nucleic acid amplification test to determine positive versus negative test results.

